10.3 Study Populations

- Intent-to-Treat Analysis Set – The ITT will include all randomized subjects. Subjects in the ITT will be analyzed as randomized.
- Per Protocol Set – The PP set will include subjects in the ITT who do not have significant protocol deviations that affect the primary endpoint. Protocol deviations will be assessed prior to database lock and unmasking. Subjects in the PP set will be analyzed as treated.
- [REDACTED]
- Safety Set – The safety set will include all subjects who have received at least 1 dose of the IP. Subjects in the safety population will be analyzed as treated.

10.4 Unit of Analysis

The study eye will be used for all monocular analyses. The fellow eye will inherently be included in all binocular analyses. Both eyes will be displayed and analyzed for all ophthalmic safety variables.

The study eye will be defined as the eye that meets all enrollment criteria. If both eyes meet all enrollment criteria, then the eye with the worse Visit 2 (Day 1) BCVA at 40 cm will be the study eye. If both eyes have the same BCVA at 40 cm, the right eye will be the study eye.

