5.1 Inclusion Criteria

Subjects must:

1. [REDACTED]
4. Have BCVA at 40 cm ≥ 0.40 and ≤ 0.90 logarithm of the minimum angle of resolution (LogMAR, approximately between 20/50 and 20/160 Snellen) in at least 1 eye at visit 1 prior to placebo dosing and in the same eye at visit 2 (pre-treatment);
5. Have between -4.50 to +2.00 diopter (D) of sphere in each eye determined by manifest [REDACTED]

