8.1.6 Methods for Assignment to Treatment Groups

Each subject who signs an ICF will be assigned a subject number (a five-digit number starting with the 2-digit site number followed by a sequential three-digit number starting with 001). Once a subject meets all qualification criteria at visit 2, he/she will be randomized in a 1:1:1 ratio via an interactive response technology system to 1 of 3 treatment groups: 1: CSF-1, 2: pilocarpine hydrochloride alone, 3: diclofenac sodium alone, and stratified by iris color (brown versus light [i.e. blue, green, gray, and hazel]) and by baseline manifest refraction spherical equivalent (-4.5 D to <-0.5 D, -0.5 D to +0.75 D, and >+0.75 D to +2.0 D); randomization will not be stratified by site.

Randomization will be used to avoid bias in the assignment of subjects to treatment, to increase the likelihood that known and unknown subject attributes (e.g. iris color and baseline characteristics) are evenly balanced across treatment groups, and to enhance the validity of statistical comparisons across treatment groups. Double-masked treatment will be used to reduce the potential of bias during data collection and the evaluation of clinical endpoints.

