10 STATISTICAL HYPOTHESES AND METHODS OF ANALYSES

10.1 General Considerations

In general, quantitative/continuous data will be summarized using descriptive statistics (n, mean, standard deviation [SD], median, minimum, and maximum). Qualitative/categorical data will be

summarized using frequencies and percentages. Statistical testing, unless otherwise indicated, will be performed at a 2-sided 0.05 significance level.

For all variables, baseline is defined as the pre-randomization measurement taken at Visit 2 (Day 1). If the measurement is not available from Visit 2 (Day 1), then the measurement from screening Visit 1 (Day -1 to -14) will be used as baseline for all treatments/visits. Change from baseline will be calculated as follow-up measure minus baseline measure.

The primary analyses of the primary and secondary endpoints will be conducted in the PP, include observed data only, and use statistical models, which adjust for the correlation between treatments within an eye and/or subject.

The secondary analyses of the primary and secondary endpoints will be conducted in the ITT, include observed data only, and use similar statistical models as the primary analyses. No subject data will be excluded from the ITT due to protocol violations/deviations. Sensitivity analysis on the primary efficacy variable will be performed on both the PP and ITT imputing missing data as failures;

Safety analyses will be conducted in the safety population.

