10.5 Efficacy Endpoints

10.5.1 Primary Efficacy Endpoint

The percentage of subjects with a ≥ 3 -line (15 letter) gain in BCVA at 40 cm, 1-hour post-treatment at visit 3 and visit 4 from the baseline measurement

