10.7 Sample Size

Fifty subjects per each of the 3 treatment arms (150 total), yields an 85% power to establish superiority of CSF-1 (0.4%/0.006%) and Pilocarpine (0.4%) to diclofenac sodium 0.006% alone in the percentage of study eyes demonstrating a ≥ 3 -line (15-letter) gain in BCVA at 40 cm, 1-hour post-treatment from the baseline measurement using a Pearson chi-squared test at a 2-sided $\alpha = 0.05$ assuming that the diclofenac sodium 0.006% alone response is 5% and the CSF-1 response is 27%, resulting in an overall 2-sided $\alpha = 0.10$ that accounts for the 2 tests of hypotheses utilizing Bonferroni correction procedures.

At least approximately 30% of subjects will have light (i.e. blue, green, gray, and hazel) iris and at least approximately 30% will have a brown iris. The actual percentages will vary based on enrollment.

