8.1 Unit of Analysis

The study eye will be used for all monocular analyses. The fellow eye will inherently be included in all binocular analyses. Both eyes will be displayed and analyzed for all ophthalmic safety variables. The study eye will be defined as the eye that meets all enrollment criteria. If both eyes meet all enrollment criteria,

then the eye with the worse Day 1 BCVA at 40 cm will be the study eye. If both eyes have the same BCVA at 40 cm, then the right eye will be deemed the study eye.

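### When both eyes qualify, the Visit 2 reading that picks the worse eye is also the baseline, so regression to the mean raises the 3-line responder rates in every arm and, if the drug works, modestly raises the percentage difference from diclofenac

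*Protocol*

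**What the plan says.** **Choice of eye.** Protocol 10.4 deals with subjects whose two eyes both meet the criteria: "then the eye with the worse Visit 2 (Day 1) BCVA at 40 cm will be the study eye". Ties go to the right eye. The synopsis has the same rule, and SAP 8.1 repeats it: "then the eye with the worse Day 1 BCVA at 40 cm will be the study eye".

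**Baseline.** In Protocol 10.1, "baseline is defined as the pre-randomization measurement taken at Visit 2 (Day 1"), with Visit 1 as the fallback only when the Visit 2 value is missing. SAP 8.3 agrees.

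**Endpoint.** Protocol 10.5.1 counts study eyes with a 3-line "gain in BCVA at 40 cm, 1-hour post-treatment at visit 3 and visit 4 from the baseline measurement".

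**A second pre-treatment reading exists.** Inclusion criterion 4 (Protocol 5.1) requires near BCVA within 0.40 to 0.90 logMAR "in at least 1 eye at visit 1 prior to placebo dosing and in the same eye at visit 2 (pre-treatment").

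The visible text does not mention regression to the mean from the eye rule. It gives no test-retest SD, no between-eye correlation, and no expected share of subjects with two eligible eyes.

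**The concern.** One reading does two jobs. Each Visit 2 reading is true acuity plus error. Taking the worse of two such readings favours the eye whose error ran in the poor direction. That error is then subtracted as part of baseline, but it does not recur at Visits 3 and 4, so the eye appears to gain letters whatever drop it receives.

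For mean change this would cancel between arms. The primary variable, however, is a percentage at a fixed 15-letter cut-off. A common shift carries more subjects across the cut-off where the response curve is steep (near 27%) than where it is flat (near 5%). The hypotheses are written as differences in percentages, and SAP 12.1 reports confidence intervals for each group and for the difference. Those are the outputs that move. In a Phase 2b trial such rates may well be carried into later planning.

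**Working it through.** **1. The plan's own figure.** Protocol 10.7: "Fifty subjects per each of the 3 treatment arms (150 total), yields an 85% power", for 5% against 27% by Pearson chi-squared, two-sided alpha 0.05. The mean rate is 0.16.

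z = [0.22 × √50 − 1.960 × √(2 × 0.16 × 0.84)] / √(0.05 × 0.95 + 0.27 × 0.73) = (1.556 − 1.016) / 0.4946 = 1.091

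Power is 86.2%, which agrees with the stated 85%.

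**2. Size of the baseline error.** Let σ be the SD of one reading's error, and D the difference between the two eyes' readings. The mean error of the eye that reads worse is √(2/π) × σ² / SD(D), where Var(D) = 2τ²(1 − ρ) + 2σ².

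Assumptions, none in the documents: SD of true acuity τ = 0.12 logMAR, between-eye correlation ρ = 0.70 to 0.95, σ = 0.03 to 0.07. A letter is 0.02 logMAR.

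| σ | ρ | SD(D) | Shift, logMAR | Letters (formula) | Letters (simulated) |
|---|---|---|---|---|---|
| 0.03 | 0.70 | 0.1022 | 0.0070 | 0.35 | 0.36 |
| 0.05 | 0.85 | 0.0965 | 0.0207 | 1.03 | 1.05 |
| 0.07 | 0.95 | 0.1060 | 0.0369 | 1.84 | 1.85 |

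**3. Effect on the rates if every subject has two eligible eyes (upper range).** Assume an SD of true gain of 0.10 logMAR, the same additive drug effect under either eye rule, and no covariate. The SD of measured gain is √(2σ² + 0.10²). In the middle row this is 0.1225, so the shift is 0.0207 / 0.1225 = 0.169 SD. By the normal approximation:

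- Active: Φ(−0.613 + 0.169) = 32.8%
- Diclofenac: Φ(−1.645 + 0.169) = 7.0%

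Simulation allows for the smaller error variance after selection. With a right-eye rule calibrated to 27% and 5%, it gives 32.5% against 6.6% in the middle case, a difference of 25.8 points. Over all scenarios it gives 29.2-35.4% against 5.7-7.5%, a difference of 23.5-27.9 points.

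**4. Effect with the eligibility window applied.** In these runs 65-83% of subjects have two eligible eyes.

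| Error SD / between-eye SD | Active | Diclofenac | Difference |
|---|---|---|---|
| 0.03 / 0.10 | 28.7% | 5.5% | 23.2 |
| 0.05 / 0.10 | 30.4% | 6.0% | 24.4 |
| 0.07 / 0.10 | 31.6% | 6.4% | 25.2 |
| 0.07 / 0.06 | 33.0% | 6.8% | 26.2 |
| 0.10 / 0.10 | 32.2% | 6.5% | 25.7 |

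A second set of runs, set up slightly differently, reaches 33.6% against 6.9% (26.7 points). When the eye is selected on Visit 1 and Visit 2 is kept as baseline, the runs in the table give 26.6-26.9% and 4.9-5.0%.

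**5. What does not move.**

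- With no drug effect, both arms rise equally. The exact chi-squared rejection rate is 4.5-4.6% at the shifted common rate, against 4.3% at 5%. Both are below the nominal 5%.
- The between-arm difference in mean letters is unchanged.
- The odds ratio goes from (0.27/0.73) / (0.05/0.95) = 7.03 to (0.325/0.675) / (0.066/0.934) = 6.81 in the middle case of step 3.

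**6. If 27% and 5% already include the shift.** Removing it gives:

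| Shift removed | Active | Diclofenac | Difference | Power |
|---|---|---|---|---|
| 0.064 SD | 24.9% | 4.4% | 20.6 | 84% |
| 0.17 SD | 21.7% | 3.5% | 18.2 | 79% |
| 0.26 SD | 19.1% | 2.8% | 16.3 | 75% |

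**The case against.** **The rule is common to all arms.** It is applied before treatment, and then "he/she will be randomized in a 1:1:1 ratio via an interactive response technology system", under masking and against a concurrent control. A reader might infer that the rule manufactures a difference from diclofenac or inflates the false-positive rate. It does neither: with no drug effect the difference stays at zero. This part of the objection stands in full, and the success criterion (rejecting H01 or H02) is not compromised.

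**The direction depends on the scale.** A reader might infer that the treatment effect is overstated generally. The synopsis model is logistic, and on the odds-ratio scale the effect falls slightly. Only the percentage difference rises, and only if the drug is active. That scale still matters because the hypotheses are stated on it.

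**The size is small and rests on outside inputs.** The error SD, the between-eye spread, the SD of true gain and the share with two eligible eyes are all assumed. A rise of about 1 to 5 points is small against the planned precision: the 95% half-width at 50 per arm is 1.96 × √(0.2446/50) = 13.7 points. This stands, although a bias does not average out as sampling error does.

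**27% and 5% may already contain the shift.** The documents do not say how these rates were derived. If they came from data with a similar eye rule, the trial would not read above plan. One cannot therefore say that the plan's rates are wrong, only that they depend on the rule.

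**Baseline is a covariate.** It may reduce the effect. It would not clearly remove it from the reported percentages, but none of these calculations includes it, and the detailed model text in Protocol 10.9.1 is redacted, as is much of SAP 12.1.

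**Conclusion.** The concern holds in a limited form. The documents show that one Visit 2 reading both picks the study eye and serves as its baseline, so 3-line response rates are biased upward in every arm. If the drug is active, the absolute difference from diclofenac is modestly raised as well.

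Under assumed single-reading SDs of 0.03 to 0.10 logMAR, and taking 27% and 5% as free of selection, the reported rates would be about 29-34% and 5.5-7%, and the difference about 23-27 points rather than 22. If the planning rates already include the shift, the selection-free rates are lower, by the amounts in step 6.

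The direction for within-arm rates follows from the documents; the size does not. The documents give no ground for doubting the randomized test, the type I error or the mean letter difference. This is a cheap improvement to the estimates, not a flaw in the trial's decision rule.

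**What to change.** **If eyes are not yet assigned.** In Protocol 10.4, the synopsis and SAP 8.1, define the study eye, when both eyes qualify, as the one with the worse Visit 1 pre-placebo BCVA at 40 cm, right eye if tied. Keep Visit 2 as baseline. Criterion 4 already requires the Visit 1 reading, so the cost is one sentence in each place and no new measurement. The correction relies on reading errors at the two visits being independent.

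**If eyes are already assigned.** Keep the planned study eye and add a sensitivity analysis of the primary variable with that eye's Visit 1 pre-placebo reading as baseline. In simulation this also returned about 27% and 5%. It needs no fellow-eye data. Re-selecting eyes afterwards would need monocular post-dose readings in the fellow eye, and the redacted assessment schedule does not show whether these exist.

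**Downside.** The study eye will sometimes not be the worse eye on Day 1, and the reported percentages become slightly less favourable.

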10.5 Efficacy Endpoints

10.5.1 Primary Efficacy Endpoint

The percentage of subjects with a ≥ 3 -line (15 letter) gain in BCVA at 40 cm, 1-hour post-treatment at visit 3 and visit 4 from the baseline measurement

10.5.2 Secondary Efficacy Endpoints

The secondary efficacy endpoints are:

- [REDACTED]
- Percentage of subjects with a ≥ 2 -line (10 letter) gain in BCVA at 40 cm [REDACTED] at visit 3 and visit 4
- [REDACTED]

10.6 Safety Endpoints

The safety endpoints are:

- BCVA
- Best-corrected low luminance distance VA
- Slit lamp biomicroscopy
- Conjunctival redness grading
- IP drop comfort assessment
- IOP
- AEs (reported, elicited, and observed)

10.7 Sample Size

Fifty subjects per each of the 3 treatment arms (150 total), yields an 85% power to establish superiority of CSF-1 (0.4%/0.006%) and Pilocarpine (0.4%) to diclofenac sodium 0.006% alone in the percentage of study eyes demonstrating a ≥ 3 -line (15-letter) gain in BCVA at 40 cm, 1-hour post-treatment from the baseline measurement using a Pearson chi-squared test at a 2-sided $\alpha = 0.05$ assuming that the diclofenac sodium 0.006% alone response is 5% and the CSF-1 response is 27%, resulting in an overall 2-sided $\alpha = 0.10$ that accounts for the 2 tests of hypotheses utilizing Bonferroni correction procedures.

At least approximately 30% of subjects will have light (i.e. blue, green, gray, and hazel) iris and at least approximately 30% will have a brown iris. The actual percentages will vary based on enrollment.

10.8 Demographic and Baseline Characteristics

Subject demographics including age, gender, race, ethnicity, and iris color will be presented using summary statistics (mean, SD, minimum, maximum, and median).

10.9 Efficacy Analysis

10.9.1 Primary Efficacy Analyses

The primary efficacy variable in this study is the percentage of study eyes with a ≥ 3 -line (15-letter) gain in BCVA at 40 cm, 1-hour post-treatment at visit 3 and/or visit 4 from the baseline measurement. The primary analysis will use the PP population on observed data only. The primary analyses will be completed using Bonferroni alpha adjustment to maintain the overall Type I error as detailed in the hypothesis section with statistical inference made on the comparisons between CSF-1 (0.4%/0.006%) versus diclofenac sodium 0.006% and between Pilocarpine (0.4%) versus diclofenac sodium 0.006%. Again as detailed in the hypothesis section, only if the higher dose concentrations, for CSF-1 (0.4%/0.006%) and/or Pilocarpine (0.4%), respectively, are successful will the corresponding lower dose concentrations, for CSF-1 (0.2%/0.006%) and/or Pilocarpine (0.2%), respectively, have inference made on the statistical test.

[Redacted]

- | [Redacted]
- | [Redacted]
- | [Redacted]
- | [Redacted]
- | [Redacted]

[Redacted]

10.9.2 Secondary Efficacy Analysis

[REDACTED]

10.10 Safety Analysis

Verbatim descriptions of AEs will be mapped to Medical Dictionary for Regulatory Activities (MedDRA) terms and be presented in a data listing. Treatment emergent AEs (TEAEs), those that occur after the first dose of IP within each period, will be summarized by treatment group using frequency and percent for each system organ class (SOC) and preferred term (PT) within each SOC. Similar summaries will also be presented for TEAEs related to the IP and by severity. When reporting the incidence of AEs, a subject will only be counted once if they ever experience an event within the SOC and ever experience the individual PT within the specific treatment period. AEs will be reported separately by period.

[REDACTED]

Full details of the safety analyses will be specified in the formal SAP.

10.11 Interim Analysis

An interim analysis may be provided when approximately 50% of the subjects have completed the study. If an interim analysis is completed, O'Brien-Fleming alpha spending function will be used to specify the interim boundaries for stopping for efficacy and for non-binding futility as well as adjusting the final 2-sided alpha level.

10.12 Missing Data

Sensitivity analysis on the primary efficacy variable will be performed on both the PP and ITT imputing missing data as failures; additional sensitivity analyses such as pattern mixture model multiple imputation methodologies and tipping point analyses may be performed and will be specified in the SAP.

10.13 Adjustment for Multiplicity

For the primary hypotheses, the study will be considered a success if either of the null hypotheses, H_{01} or H_{02} , are rejected in favor of their corresponding alternative hypotheses, H_{11} or H_{12} . The overall Type I error of the 2-sided alpha = 0.10 will be preserved through the use of Bonferroni correction procedures testing each hypothesis at a 2-sided alpha = 0.05.

Again as detailed in the hypothesis section, only if the higher dose concentrations, for CSF-1 (0.4%/0.006%) and/or Pilocarpine (0.4%), respectively, are successful will the corresponding lower dose concentrations, for CSF-1 (0.2%/0.006%) and/or Pilocarpine (0.2%), respectively, have inference made on the statistical test. Within these hierarchical frameworks, these hypotheses can be tested at a 2-sided alpha = 0.05 while still preserving an overall Type I error of alpha = 0.10.

There will be no adjustment for multiplicity for testing of secondary endpoints.

11 COMPLIANCE WITH GOOD CLINICAL PRACTICES, ETHICAL CONSIDERATIONS, AND ADMINISTRATIVE ISSUES

This study will be conducted in compliance with the protocol, current GCPs, including the ICH Guidelines, and will, in general, be consistent with the Declaration of Helsinki. In addition, all applicable local, state, and federal requirements relevant to the use of IPs in the countries involved will be adhered to.

11.1 Protection of Human Subjects

11.1.1 Subject Informed Consent

Informed consent must take place before any study-specific procedures are initiated. Signed and dated written informed consent must be obtained from each subject and/or from the subject's parent or legal guardian prior to enrollment into the study.

All ICFs must be approved for use by the sponsor and receive approval/favorable opinion from an IRB prior to their use. If the ICF requires revision (e.g. due to a protocol amendment or

significant new safety information), it is the investigator's responsibility to ensure that the amended informed consent is reviewed and approved by [REDACTED] prior to submission to the governing IRB and that it is read, signed, and dated by all subjects subsequently enrolled in the study as well as those currently enrolled in the study.

If informed consent is taken under special circumstances (oral informed consent), then the procedures to be followed must be determined by [REDACTED] and/or the sponsor and provided in writing by [REDACTED] and/or the sponsor prior to the consent process.

11.1.2 IRB Approval

This study is to be conducted in accordance with IRB regulations (U.S. 21 CFR Part 56.103). The investigator must obtain appropriate IRB approval before initiating the study and re-approval at least annually.

Only an IRB-approved version of the ICF will be used.

11.2 Ethical Conduct of the Study

This study will be conducted in accordance with the ethical principles that originated with the Declaration of Helsinki.

11.3 Subject Confidentiality

All personal study subject data collected and processed for the purposes of this study should be maintained by the investigator and his/her staff with adequate precautions as to ensure that the confidentiality of the data is in accordance with local, state, and federal laws and regulations.

Monitors, auditors and other authorized representatives of [REDACTED] the sponsor, the IRB approving this study, the FDA, the Department of Health and Human Services, other domestic government agencies, and other foreign regulatory agencies will be granted direct access to the study subject's original medical and study records for verification of the data and/or clinical trial procedures. Access to this information will be permitted to the aforementioned individuals to the extent permitted by law.

A report of the results of this study may be published or sent to the appropriate health authorities in any country in which the IP may ultimately be marketed in, but the subject's identity will not be disclosed in these documents.

11.4 Documentation

Source documents may include a subject's medical records, hospital charts, clinic charts, the investigator's subject files, as well as the results of diagnostic tests such as X-rays, laboratory tests, and electrocardiograms. The investigator's copy of the eCRFs serves as the investigator's record of a subject's study-related data.

11.4.1 Retention of Documentation

All study-related correspondence, patient records, consent forms, records of the distribution and use of all IPs, and copies of case report forms should be maintained on file for at least 2 years after the last approval of a marketing application in an ICH region and until there are no pending or contemplated marketing applications in an ICH region; or until at least two years have elapsed since the formal discontinuation of clinical development of the IP. These documents will be retained for a longer period if required by the applicable regulatory requirements or by an

agreement with the sponsor. It is the responsibility of the sponsor to inform the investigator/institution as to when these documents no longer need to be retained.

If the responsible investigator retires, relocates, or for other reasons withdraws from the responsibility of keeping study records, custody must be transferred to a person who will accept the responsibility. The sponsor must be notified in writing of the name and address of the new custodian.

11.5 Labeling, Packaging, Storage, Accountability, and Return or Disposal of Investigational Product

